#### 181 VII. Data collection

182

A. Screening and enrollment (registration) into the study (in person; ~40 minutes). The ED 183 coordinator, a member of the research team, at each Clinical Center screened patients in the ED, 184 185 Urgent Care, or Observation Unit after treatment initiation for asthma exacerbation and before discharge. The ED coordinator obtained verbal assent from the ED clinician prior to approaching 186 the child/caregiver for informed consent. Following informed consent, the ED coordinator 187 obtained Baseline data, registered the patient in a customized, secure, on-line CHICAGO Plan 188 REDCap portal developed by the DCC, then obtained the treatment assignment (ED-only, ED-189 plus-home, or Enhanced usual care). The ED Coordinator offered to arrange the date/time of the 190

- 191 l-month follow-up visit (see below).
- 192

B. 1-month follow-up contact after discharge (telephone; ~15 minutes). Post-baseline data
collection was performed by the DCC Research Assistant, who was masked to treatment
assignment. The Research Assistant conducted a telephone interview to assess outcomes
approximately 1 month after discharge. The interview was also designed to collect / update
contact information and to promote retention in the CHICAGO Plan. The DCC Research Assistant
arranged date/time of the 3-month follow-up visit (see below), or inquired about the best time to
call again.

200

C. 3-month follow-up contact after ED discharge (telephone; ~15 minutes). The DCC Research
Assistant, masked to treatment assignment, conducted a telephone interview to assess outcomes
approximately 3 months after ED discharge. The interview was also designed to collect / update
contact information and to promote retention in the CHICAGO Plan. The DCC Research Assistant
arranged date/time of the 6-month follow-up visit (see below), or inquired about the best time to
call again.

- 207
- 208 D. 6-month follow-up contact after discharge (in person or by telephone; ~40 minutes). The DCC
- 209 Research Assistant, masked to treatment assignment, conducted a study visit in person or via
- telephone (per participant preference) to assess outcomes approximately 6 months after discharge.
- 211 The in-person visit afforded the ability to conduct an assessment of home trigger avoidance;

review inhaler technique; and assess cACT (child) and PACQLQ, which are more easily collected 212 during in-person visits. 213

- 214

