#### 221 **VIII.** Outcomes

- 222
- The selection of primary outcomes was based on several criteria: 1) patient-centeredness, defined 223
- as domains identified as important by children and their caregivers; as described in our previous 224
- publications; 2) availability of validated measures in English and in Spanish that could be 225
- administered in person and by phone; 3) plausibility that such measures could be responsive to an 226
- effective intervention in the target population; and 4) limited burden (e.g., time) for study 227
- participants. On this basis, we selected two NIH Patient-Reported Outcomes Measurement 228
- Information System (PROMIS) measures as primary outcomes (1 for the child and 1 for the 229
- caregiver). Several measures were selected for secondary outcomes to address recommendations of 230
- 231 national asthma guidelines, expressed preferences of caregivers and other stakeholders, and to
- compare results of the CHICAGO Plan with previous studies. 232
- 233
- A. Primary outcomes 234

1. The change in asthma impact at 6 months compared to the baseline assessed in the ED served as 235 the primary outcome in children. In children 5 to 7 years, we assessed asthma impact using the

- 236 PROMIS Parent Proxy Short Form v1.0 – Asthma Impact 8a. In children 8 to 11 years, we used
- 237
- the PROMIS Pediatric Short Form v1.0 Asthma Impact 8a. 238
- 239
- 2. The change in Satisfaction with Participation in Social Roles at 6 months compared to the 240
- baseline assessed in the ED served as the primary outcome in the caregiver. We used the PROMIS 241 Short Form v1.0 – Satisfaction with Participation in Social Roles 4a. 242
- 243
- 244 B. Secondary outcomes
- For children: 245
- 246 1) The Childhood Asthma Control Test (cACT) at 6 months compared to the baseline assessed in the ED 247
- 2) Acute care visits at 6 months (number of all-cause urgent care visits, ED visits, 248
- hospitalizations, using electronic health records) 249
- For caregivers: 251
- 252 1) Pediatric Asthma Caregiver's Quality of Life Questionnaire (PACQLQ) at 6 months compared to the baseline assessed in the ED 253
- 2) NIH PROMIS measures for anxiety, depression, fatigue, sleep disturbance at 6 months 254 compared to the baseline assessed in the ED 255
- 256 257

- 258 Indicators of guideline-consistent asthma care provided on ED discharge:
- 1) Systemic corticosteroids prescribed for use at home (yes/no)

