#### 270 IX. Analysis plan

271

269

- All primary and secondary outcomes were analyzed according to the intention-to-treat principle.
- All randomized subjects were included in the primary analysis, unless subjects were terminated
- due to ineligibility. Baseline sociodemographic and clinical characteristics in the intervention and
- control groups were compared using the frequency and percentages for categorical variables and
- 276 median with inter-quartile or mean with standard error for continuous variables. For bivariate
- analyses, the pairwise comparisons between three intervention arms for the change in primary and
  some secondary outcomes from baseline to 3 or 6 months were tested by Wilcoxon rank sum test.
- The W statistic, p-value and mean rank were reported together with horizontal mirror bar plots. For
- primary outcomes, a statistical significance occurred when p-value was less than 0.0167 after
- Bonferroni correction for three pairwise comparisons (0.05/3). In addition, chi-square tests were
- also conducted for other secondary outcomes.
- 283
- To address missing data in the analyses, we checked the missing completely at random (MCAR) assumption and then employed a multiple imputation strategy. Using a logistic regression method described in Hedeker & Gibbons (2006), we found that the current outcome missingness was not statistically associated with previous observed outcomes across time. Additional characteristics comparisons between participants with and without missing primary outcomes across time was also done using Chi-square tests for categorical variables and Mann-Whitney U test for continuous
- variables. No statistical difference was observed between the two groups (i.e. with and without
- 290 variables. No statistical difference was observed between the two groups (i.e. with and without 291 missing primary outcomes). We therefore used a fully conditional specification (FCS) approach to
- impute the missing values with variables of interest in the primary analysis models for 30
- 293 imputations. The raw and imputed data had similar distributions (mean, standard deviation,
- 294 minimum and maximum values).

- 296 Since the two primary outcomes were not normally distributed and our data satisfied the MCAR
- assumption, we used generalized estimating equations (GEE) to examine the effect of intervention
- group on outcomes at 3 and at 6 months compared to that of the enhanced usual care group using

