- ordinal logistic regression models; the continuous dependent variables were categorized into
- quartiles. The main predictors of the unadjusted GEE models were time (0, 1, 3, and 6 months),
- intervention group, and their interactions. In an adjusted model, we added pre-specified covariates
- 302 including, race (Black vs. non-Black), ethnicity (Latino vs. non-Latino), gender (boy vs. girl),

health insurance (Public aid vs. Other), site enrolled (sites 1 to 6), number of all-cause acute care

use in the 12 months prior to enrollment (at least one vs. none). To access the intervention effect

between groups across time, we reported our results as odds ratios (ORs for higher quartiles) of

- interactions between study group and time and their 98% confident intervals [CIs; corresponding
   to a 2-sided alpha=0.0167) to account for Bonferroni adjustments for the three pairwise
- 307 to a 2-sided alpha=0.0167) to account for Bonferroni adjustments for the three pairwise 308 comparisons.
- 309

310 In secondary analyses, we explored heterogeneity of treatment effects by adding a three-way

interaction between intervention, time, and a subgroup factor in the model described previously.

312 Pre-specified subgroup factors included race (Black vs. non-black), ethnicity (Latino vs. non-

Latino), gender (boy vs. girl), and number of all-cause acute care use in the 12 months prior to enrollment (at least one vs. none).

315

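### No described treatment-effect analysis conditions on the baseline score: a modest, avoidable loss of precision (10% of variance at the plan's correlation of 0.80), not bias

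*Combined protocol and SAP*

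**What the plan says.** Section VIII.A defines the child primary outcome as a change: "The change in asthma impact at 6 months compared to the baseline assessed in the ED served as" the primary outcome. The caregiver outcome has the same form.

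Section IX then describes two treatment-effect analyses.

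- **Wilcoxon rank sum tests.** These cover "the pairwise comparisons between three intervention arms for the change in primary and" some secondary outcomes, from baseline to 3 or 6 months. The quantity ranked is raw change.
- **Ordinal GEE.** The stated reason begins "Since the two primary outcomes were not normally distributed and our data satisfied the MCAR" assumption. The models are "ordinal logistic regression models; the continuous dependent variables were categorized into" four ordered groups cut at the quartiles. On the model terms, section IX states: "The main predictors of the unadjusted GEE models were time (0, 1, 3, and 6 months". Group and the group-by-time interactions are the other terms. The reported effects are odds ratios for "interactions between study group and time and their 98% confident intervals".

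The adjusted model adds covariates "including, race (Black vs. non-Black), ethnicity (Latino vs. non-Latino), gender (boy vs. girl", then insurance, site and prior-year acute care use. The subgroup model adds a three-way interaction to the same model. No baseline score is named in any of these.

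Section VII.A gives the order of events. The ED coordinator "obtained Baseline data, registered the patient in a customized, secure, on-line CHICAGO Plan" portal, and only then obtained the treatment assignment.

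**The concern.** Under randomisation, a difference between arms in the baseline score is chance. Raw change subtracts the whole of that difference, whereas the best prediction of the 6-month score uses only the fraction given by the correlation. A GEE with a free arm effect at time 0 and a group-by-time odds ratio does the same on the log-odds scale. Both contrasts therefore carry baseline noise that could be removed.

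The score precedes assignment, so it is a valid covariate. It is already collected, and it is half of the declared endpoint. At stake is the width of the confidence intervals, with alpha already reduced to 0.0167 and the scores cut into quartiles.

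**Working it through.** **Inputs.** From the power paragraph of section IX: within-individual correlation 0.80; two-sided alpha 0.05/3 = 0.0167 (z = 2.394); power 80% (z = 0.842); difference 0.35 SD; design effect 2; R2 0.15; four measurements; evaluable 0.80 × 640 = 512, or 170.7 per arm; required total 426. Assumed here: equal SD at baseline and 6 months.

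**1. The plan's 426.** The method is a two-group Hotelling T-squared calculation. The documents give no effect profile over time, so I assume a rise that is linear in months: δ = 0.35 × (0, 1/6, 1/2, 1). With equal correlation 0.80:

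δ′R⁻¹δ = 5 × [0.1225 × 1.2778 − (0.8/3.4) × 0.1225 × 2.7778] = 0.382

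Dividing by 1 − 0.15 gives 0.450. With 71 per arm the noncentrality is 71/2 × 0.450 = 15.97 on 4 and 137 df, and power is 80.0%. Then 71 × 2 (design effect) × 3 arms = 426. The match is not unique: other assumed profiles give 312 to 438, or 1,104 if the difference is also present at baseline. So 426 does not show which contrast was powered.

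**2. Variance with and without the baseline score** (SD² units, per person):

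- change score: 2(1 − ρ)
- baseline-adjusted: 1 − ρ²
- proportional saving: (1 − ρ)/2

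| ρ | change | adjusted | variance saved | SE saved |
|---|---|---|---|---|
| 0.80 (plan) | 0.40 | 0.36 | 10% | 5.1% |
| 0.70 (assumed) | 0.60 | 0.51 | 15% | 7.8% |
| 0.50 (assumed) | 1.00 | 0.75 | 25% | 13.4% |
| 0.30 (assumed) | 1.40 | 0.91 | 35% | 19.4% |

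**3. Power at 512 evaluable, no R2 credit.** Power = Φ(0.35/√(2 × v × 2/170.7) − 2.394).

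- v = 0.40: 0.35/0.0968 − 2.394 = 1.22, power 88.9%.
- v = 0.36: 0.35/0.0919 − 2.394 = 1.42, power 92.2%.

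At 426 evaluable the same formula gives 81.7% and 86.0%. Total N for 80% power is 3 × 2 × v × 2 × (3.236/0.35)², about 410 for change and 369 for the adjusted contrast. At an assumed ρ of 0.5, power at 512 is 46% and 60%.

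**4. Quartile GEE.** I use simulated latent normal scores at 0 and 6 months, 142 per arm, 1,500 runs, quartile cuts pooled over visits and a proportional-odds model. Making full use of the equality of arms at time 0 lowers the variance of the interaction log odds ratio by 12% (effect 0.35 SD) to 15% (no effect) at ρ = 0.80, or 6-8% in SE. At ρ = 0.5 the reduction is 25-28%.

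**5. Wilcoxon test.** I simulate normal scores at 85 per arm (170.7/2), 10,000 runs.

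| ρ | Wilcoxon on change | ANCOVA | rank ANCOVA |
|---|---|---|---|
| 0.80 | 86.4% | 91.1% | 86.9% |
| 0.50 (assumed) | 42.3% | 58.3% | 54.7% |

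**6. Bias.** With no effect, the mean interaction log odds ratio was −0.005 (ρ = 0.80) and 0.000 (ρ = 0.5). With a true linear effect of 0.35, mean estimates were 0.353 (change) and 0.351 (adjusted).

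**The case against.** The case for leaving the plan alone is fair. Change is the declared outcome and both analyses match it. On the plan's inputs the change contrast needs about 410 participants, fewer than the 426 required and the 512 expected, and adjustment adds about three points of power. The analyses are already complete, so anything added is post hoc. The covariate list is introduced as inclusive, so it may not be exhaustive. With normal scores at 0.80, the rank-based adjustment hardly improves on the Wilcoxon test. All of this stands, and it limits the point to a supplementary analysis. It does not show that the baseline score is conditioned on anywhere. The score may enter the imputation model, but that is not adjustment of the treatment contrast.

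Four stronger readings are tempting and not supported.

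- **The planned analyses are biased.** Baseline precedes assignment, so an imbalance is chance and averages out. It adds noise in a given sample.
- **The trial is underpowered for this reason.** That needs a correlation well below 0.80. A baseline taken during an exacerbation might predict 6-month scores less well, but no observed value is given.
- **The R2 of 0.15 offsets or enlarges the loss.** If demographics act on the stable person level, they leave the change variance unchanged (0.399 before and after adjustment, simulated) and cut the baseline-adjusted variance only from 0.359 to 0.352. An unadjusted Wilcoxon test can earn no such credit. Hence none is used in steps 3 to 5.
- **The Wilcoxon test is preferable to the quartile GEE.** In simulation with normal scores at 0.80 it had more power than a GEE with the baseline score added (86% against 79%). At 0.5 the order reverses (42% against 48%), and the plan says that the scores were not normal.

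**Conclusion.** The point holds as an efficiency matter. No described treatment-effect analysis conditions on a baseline score that was available before assignment. At the plan's correlation of 0.80 the avoidable loss is 10% of variance and 5% of SE on the linear scale, about three points of power at 512 evaluable (89% to 92%), and about 12-15% of variance in the quartile GEE. The planned contrast still exceeds 80% power on those inputs.

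These figures rest on equal variances, equal correlation, the plan's design effect of 2 and normal underlying scores. The larger losses at lower correlations are assumptions. The planned results remain valid.

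**What to change.** Report two additions beside the planned results, both labelled post hoc.

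1. **ANCOVA of the uncategorised 6-month score** on the baseline score, arm, and the randomisation strata site and race, with robust SE. Add a rank ANCOVA as a check for non-normality. The arm coefficient is the same as in an ANCOVA of change, because subtracting baseline from the response only lowers the baseline slope by 1. The analysis therefore stays on the declared change scale. For the child outcome, let the baseline slope (and intercept) differ between the parent-proxy form (5-7 years) and the self-report form (8-11 years).

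2. **GEE with the arms constrained to be equal at time 0.** This keeps the planned group-by-time odds ratio. The plan states no working correlation, and the choice matters here. Under independence the constrained model reduces to a comparison of follow-up scores alone, with linear-scale variance 1.00 against 0.40 for change at ρ = 0.80, so precision would be lost. Use a working association that reflects the within-person correlation. Alternatively, subtract from the planned interaction log odds ratio its regression on the time-0 arm log odds ratio, using their joint robust covariance. The second route is the one behind the 12-15% figure. If the baseline score is added as a covariate instead, report that odds ratio as conditional and do not compare it with the planned one: in simulation at 0.80 the same effect gave 0.36 conditional and 0.55 planned.

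Also report the observed correlation between baseline and 6-month scores, which settles the size of the loss.

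**Cost.** Some SAP text and re-run models, with no new data. The imputation model must carry the uncategorised baseline score. The additions cannot replace the planned results.

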#### 93 Inclusion criteria (all of the following):

- Child is 5-11 years of age (a population in whom a diagnosis of asthma is generally reliable, and in whom exacerbations are common);
- Child is presenting to the ED, urgent care center, or observation unit at a participating clinical center (Anne and Robert H. Lurie Children's Hospital of Chicago, Sinai Health System's Mount Sinai Hospital, John H. Stroger Jr. Hospital of Cook County Health & Hospitals System, Rush University Medical Center, University of Chicago Medicine Comer Children's Hospital, and the University of Illinois Hospital & Health Sciences System);
- 3. Child is treated with at least 1 dose of an inhaled or nebulized short-acting bronchodilator
   (quick-relief medication);
- 4. Child received systemic corticosteroids in the ED OR the caregiver reported at least 1
  additional acute care visit for asthma in the previous 6 months (defined as an asthma-related
  ED visit or urgent care visit, or course of systemic corticosteroids);
- 106 5. Child and caregiver approached at least 1 hour after receipt of the first dose of quick-relief
- 107 medication or systemic corticosteroids, whichever occurred first;

- 108 6. Diagnosis of asthma exacerbation by treating clinician;
- 109 7. Treating ED clinician indicates the child is likely to be discharged to home;
- 110 8. Caregiver reports that English or Spanish is the preferred language at home.
- 111

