#### 166 VI. Randomization

167

168 Randomization occurred at the patient level, with permuted block sizes stratified by site and race

169 (black vs. non-black). Based on data from the Clinical Centers, we expected about 70% of enrolled

170 participants to be black, 23% to be white, and that the remainder would be mostly Asian. Of the

- 171 planned enrollment of 640 children, we expected 15% to be Hispanic/Latino. Stratification by race
- for the purposes of randomization was "Black" (those who selected Black or African American,
- includes multi-race if at least one race was Black or African American) vs. "non-Black" (American
   Indian/Alaskan Native, Asian, Native Hawaiian or other Pacific Islander, white, and multi-race if
- Indian/Alaskan Native, Asian, Native Hawaiian or other Pacific Islander, white, and mulnone are Black or African American).
- 176

The CHICAGO Plan Research Electronic Data Capture (REDCap) system for study personnel
 (available 24 hours x7 days/week) provided the random treatment assignment: ED-only, ED-plus-

- 179 home, or Enhanced usual care.
- 180

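### The child primary outcome combines parent-rated (5-7 years) and child-rated (8-11 years) scores with no age-band or form term in the design or model, which costs precision if the two forms change differently

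*Combined protocol and SAP*

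**What the plan says.** Section VIII (Outcomes, A. Primary outcomes) defines a single child endpoint: "The change in asthma impact at 6 months compared to the baseline assessed in the ED served as" the primary outcome in children. The instrument depends on age. "In children 5 to 7 years, we assessed asthma impact using the" "PROMIS Parent Proxy Short Form v1.0 – Asthma Impact 8a. In children 8 to 11 years, we used" "the PROMIS Pediatric Short Form v1.0 Asthma Impact 8a". The parent therefore rates the younger band and the child rates the older one.

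Eligibility (section IV, revised criteria) covers the whole range: "Child is 5-11 years of age (a population in whom a diagnosis of asthma is generally reliable". The expected split at age 8 is not given.

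Age band or form could have been handled in four places:

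- **Randomization (section VI):** "Randomization occurred at the patient level, with permuted block sizes stratified by site and race". Neither age nor form is a stratum.
- **Adjusted GEE (section IX):** the covariates are "including, race (Black vs. non-Black), ethnicity (Latino vs. non-Latino), gender (boy vs. girl", followed by "health insurance (Public aid vs. Other), site enrolled (sites 1 to 6), number of all-cause acute care" use in the 12 months before enrolment. Neither age nor form is named.
- **Heterogeneity analyses (section IX):** the subgroup factors are race, ethnicity, gender and prior acute care.
- **Multiple imputation (section IX):** it uses the variables of the primary models, so form is not shown to enter.

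The outcome is analysed by a Wilcoxon test on change, and by an ordinal GEE on scores cut into quartiles with arm, time and their interaction. No analysis by form is described.

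**The concern.** Who completes the form is fixed by age at enrolment, so it is known before randomization and can be adjusted for at no risk. Parents and children may report different amounts of improvement between an emergency visit and six months later. If so, part of the spread in change scores reflects the rater and not the treatment. The plan leaves that part in the error, which widens the intervals for a primary comparison already tested at 0.0167. The reader also cannot see whether an arm effect was reported by parents, by children or by both.

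**Working it through.** **Inputs from the plan (section IX, power paragraph).** Two-sided alpha 0.05/3 = 0.0167; power 80%; four measurements; within-person correlation 0.80; design effect 2; R² 0.15; target difference 0.35 SD; stated total 426; expected evaluable 512, about 171 per arm.

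**Assumptions, because the documents are silent.** Ages are spread evenly over 5-11, so p = 3/7 = 0.43 are parent-rated (range 30-50% shown for imbalance). The difference between forms in mean change, d, is varied.

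**1. The plan's own figure.** I used a two-group Hotelling T² on four visits with compound symmetry at 0.80, and assumed an effect growing linearly to 0.35 SD at 6 months. The per-arm n is multiplied by 0.85 × 2 × 3 = 5.1.
- Linear by visit: 84.2 × 5.1 = 429.
- Linear in months: 82.9 × 5.1 = 423.

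Both are within 3% of 426, so the stated figure reproduces.

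**2. Variance left in the error.** The variance of a 6-month change is 2(1 − 0.80) = 0.40 in squared baseline SDs. An unmodelled form difference adds p(1 − p)d² = 0.245d².
- Share of total change variance = 0.245d² / (0.40 + 0.245d²).
- Inflation = 1 + 0.245d²/0.40.
- Power = Φ[(2.394 + 0.842)/√inflation − 2.394].

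| d (SD) | Share | Inflation | N in place of 426 | Power |
|---|---|---|---|---|
| 0 | 0% | 1.000 | 426 | 80% |
| 0.25 | 3.7% | 1.038 | 443 | 78% |
| 0.35 | 7.0% | 1.075 | 458 | 77% |
| 0.5 | 13.3% | 1.153 | 492 | 73% |

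With change variance 1.0 in place of 0.40, the share at d = 0.5 is 6% and power is 77%. Putting d = 0.5 into the full four-visit calculation, growing over time like the treatment effect, moves 429 to 507 and 423 to 501. Every one of these totals is still below 512.

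**3. Chance imbalance in form mix.** For two arms of 171, the SD of the difference in proportions is √(2 × 0.245/171) = 0.0535.
- The 95% range is ±10.5 points (±9.7 if 30% are parent-rated, ±10.6 if 50%).
- A given pair differs by more than 10 points about 6% of the time.
- A 10-point imbalance shifts the effect by 0.10 × d: 0.025 SD at d = 0.25 and 0.05 SD at d = 0.5, against the 0.35 SD target.

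**4. A constant difference in level.** If each child keeps one form, a constant gap subtracts out of the change score. In the four-visit calculation, a 0.5 SD level gap moves 429 only to 432.

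**5. What adjustment recovers.** I simulated the Wilcoxon test on change with 171 per arm, correlation 0.80 and an assumed 0.2 SD effect. Stratifying by form raised power from about 64% to 67% at d = 0.25 and from about 59% to 67% at d = 0.5, within a point or two of simulation error. It lost nothing at d = 0. Under the null, rejection stayed near 0.0167 with and without stratification.

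**The case against.** The strongest reply is that this is one omitted prognostic covariate in a randomized comparison. The documents give no parent-child difference in level or change, and if the forms behave alike the cost is zero. Even at d = 0.5 SD, larger than the treatment effect the trial was sized for, the required total stays inside 512. All of this stands, and it limits the point to efficiency and interpretation.

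A reader might infer three stronger things that the documents do not support.

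- **That the arm comparison is biased.** Randomization makes any imbalance in form mix a matter of chance. The standard error already covers it, and type I error is unaffected.
- **That pooling distorts the quartiles.** A 0.5 SD level gap would put 34% of parent-rated but 18% of child-rated scores in a pooled top quartile. That describes level, whereas the reported effect is the arm-by-time interaction. With that gap, an assumed 0.25 SD effect and a simple test on change in quartile category standing in for the GEE, simulated power was 56% with pooled cuts and no form term. It was 57% with within-form cuts and a form term. Section IX also does not say whether the cuts were pooled.
- **That the trial can show whether the effect differs by rater.** On the simple scale, the detectable form-by-arm interaction is about 0.61 SD (171 per arm, 80% power, two-sided 0.05), well above the 0.35 SD target.

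It is also fair to say that changing the pre-specified covariates now would be post hoc. That governs how the fix is labelled, not whether it is useful.

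**Conclusion.** The point holds as a loss of precision conditional on an unknown. One child primary outcome rests on two forms with two kinds of rater, and age band or form is named in no stratum, covariate list or subgroup list. If the forms differ in mean change by 0.25 to 0.5 SD, about 4% to 13% of change variance is left unexplained, and the stated 80% power becomes roughly 78% to 73%. These sizes rest on 3/7 of children being parent-rated and on change variance 0.40 from the plan's correlation; with variance 1.0 they are less than half as large. The validity of the primary test is not in question.

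Two readings are involved. That the forms are analysed together is inferred from the single outcome and single model, since no pooling step is written out. The cancellation of a level gap assumes each child keeps the enrolment form; the documents do not say what happens when a child turns 8 during follow-up.

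**What to change.** For the child primary outcome, add form at enrolment and its interaction with time to the adjusted GEE, and include form in the imputation model. Stratify the Wilcoxon test by form. Show the 6-month arm effect separately for the parent-rated and child-rated forms, marked as descriptive, with no claim of a difference between them.

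Data collection was scheduled to end on March 31, 2017 (section XI) and this document is dated December 1, 2017. Present these results as a sensitivity analysis beside the pre-specified model and say so. State also whether any child changed form during follow-up.

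The cost is a few extra model terms and a small table. Age is an eligibility item and determines the form, so no new data are needed.
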